## INTRODUCTION

Multifocal (MF) and multicentric (MC) breast cancers are relatively common clinical entities, with incidence in the literature ranging from 6% to 60%. This large variability is due to differences in definitions used, inclusion or exclusion of *in situ* disease, and methods of pathologic sampling. Most commonly, MF breast cancer typically refers to two or more synchronous areas of disease confined within the same quadrant versus MC disease, which refers to two synchronous areas of disease within different quadrants. Regardless of the definition, the tumor with the greatest diameter is typically used for staging purposes.

As advances in preoperative imaging continue, the number of MF and MC tumors identified increases, and better guidelines for their management are needed. In particular, questions still exist regarding the optimal loco-regional (LR) therapy for MF and MC breast cancer. Multifocality and multicentricity are regularly considered as a relative contraindication for breast-conservation therapy. The reasoning for this traditional paradigm is based on two assumptions. **Firstly**, the perceived higher risk for in-breast recurrence since it is assumed that in MF/MC cancer the risk of more invasive foci in the breast is greater, and therefore radiotherapy possibly less effective. **Secondly**, the expected less good cosmetic outcome due to wide excisions and larger boost volumes with more fibrosis. Consequently, the vast majority of patients with MF/MC, either clinically detected or visible on standard imaging (mammography, ultrasound) is advised to be treated with a mastectomy. However, such a tendency towards a more extensive surgery is debated. The COMICE trial did not show any reduction of local recurrence or any improvement of long-term survival in patients undergoing preoperative MRI.

Three more recent developments may change this traditional paradigm.

جامعة

**First**, the introduction of MRI has led to the identification of more small cancer foci besides the index cancer.

**Secondly**, more effective neo-adjuvant chemotherapy result in more complete or near complete remissions or substantial reductions in the extent of cancers. **Thirdly**, improved surgery by better localization techniques and oncoplastic procedures allow for more precise and complete breast conserving resections.

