**Primary objective:**

Evaluating the application of oncoplastic surgical techniques in the surgical treatment of multifocal breast cancer as regards; successful resection of tumor burden, disease control (recurrence) and cosmetic results.

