**Secondary objectives:**

1. Determine the burden of multifocal breast cancer among Egyptian population.
2. Determine to what extent the presence of (MF) is associated with the use of mastectomy.
3. Determine the factors that are associated with the use of BCT in the presence of (MF) disease.
4. Determine whether the presence of (MF) increased the rate of local relapse in patients treated with BCT.
5. Exploring the association between multifocality and overall survival and loco-regional relapse.
6. Stating a reliable recommendations for management of multifocal breast cancer.

Handwritten signatures and initials are present at the bottom of the page, including a signature in Arabic and a signature in English.

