## PATIENTS

This study includes two groups of patients:

**Group (A):** All patients with operable breast cancer , admitted and managed at the Surgical Oncology unit, Alexandria Faculty of Medicine, between Jan.2010 to Dec.2015, their data are retrospectively reviewed and analyzed.

**Group (B):** All patients with operable multifocal breast cancer excluding those indicated for neoadjuvant therapy and those diagnosed as inflammatory breast cancer admitted between May.2017 to May.2018 will be offered oncoplastic breast conserving surgery and prospectively evaluated for 24 months as regards the outcomes of using different oncoplastic techniques to extend the clinical utility of BCT as a surgical management for multifocal breast cancer.

[name]

الدكتور

[name]

الدكتور

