## METHODS

**For group (A) patients The following data of will be included and recorded:**

- Age at diagnosis: young patients are defined as younger than 35 years.
- Surgery performed:
  - a-Breast conservation: involves lumpectomy with oncologically appropriate safety margins with either sentinel lymph node detection or axillary lymph node dissection according to the triple assessment of the patients. The introduction of different oncoplastic procedures in breast cancer surgery allows more breast conservation.
  - b-Mastectomy: modified radical mastectomy.
- Tumor characteristics: size, nodal status, presence of lympho-vascular invasion, amount of intraductal component, tumor grade, margin status, hormone receptor, and Her2 neu status(if available).
- Pathological determination of multifocal and unifocal tumors.
- The follow-up period of the patients was registered.
- The occurrence of loco-regional recurrence or distant metastases during the follow-up period was recorded and considered as an end point for follow-up.

Local recurrence is defined as recurrence in the original tumor bed (for BCS) or field of mastectomy.

Regional recurrence refers to metastatic disease in the ipsilateral axilla or supraclavicular lymph nodes or ipsilateral involvement of internal mammary nodes.

Loco-regional recurrence-free survival of patients who are pathologically multi-focal and uni-focal will be estimated using the Kaplan-Meier method and compared among different categories using log-rank tests (univariable analysis

in 4/12

([name])

of risk factors for loco-regional recurrence among multi-focal and uni-focal breast cancer patients).

Distal recurrence-free survival for both groups will be analyzed using the same test (univariable analysis of risk factors for distal recurrence).

Associations with local recurrence in uni-focal and multi-focal breast cancer patients are further evaluated using multivariable Cox proportional hazards regression model and summarized with hazard ratios 95 % confidence intervals (CIs).

Associations with distal recurrence uni-focal and multi-focal breast cancer patients will be further evaluated using multivariable Cox regression model.

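### Local recurrence after breast conservation is confined to the tumor bed, so a relapse elsewhere in the same breast is not an event for objective 4 or for the BCS part of loco-regional relapse in objective 5

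*Protocol*

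**What the plan says.** The protocol defines recurrence once, in the Methods for Group A. For the breast and chest wall: "Local recurrence is defined as recurrence in the original tumor bed (for BCS) or field of mastectomy". For the nodes: "Regional recurrence refers to metastatic disease in the ipsilateral axilla or supraclavicular lymph nodes or ipsilateral involvement of internal mammary nodes". After breast-conserving surgery (BCS), then, the local category names the tumor bed and the regional category names nodal sites. Neither document has a category for a relapse elsewhere in the treated breast or for an ipsilateral new primary.

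These definitions serve two secondary objectives. Objective 4 is: "Determine whether the presence of (MF) increased the rate of local relapse in patients treated with BCT". Objective 5 is: "Exploring the association between multifocality and overall survival and loco-regional relapse". The objectives say relapse where the Methods say recurrence. Relapse has no definition of its own, so I read the two words as one term.

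The Methods for Group B repeat the Group A sentence making loco-regional recurrence or distant metastasis an end point, but define neither. Recurrence is also part of the primary objective, which covers "successful resection of tumor burden, disease control (recurrence) and cosmetic results". The SAP lists tests for categorical data and defines no end point.

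**The concern.** The event is narrower than the question. The Introduction gives two reasons why multifocal (MF) and multicentric (MC) disease has been steered to mastectomy. The first is "the perceived higher risk for in-breast recurrence since it is assumed that in MF/MC cancer the risk of more invasive foci in the breast" being greater. That worry concerns the whole breast, and the end point counts only the part that was operated on.

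An abstractor who follows the rule would not count a relapse elsewhere in the conserved breast. If any such relapse occurred, the in-breast relapse rate after BCS is understated. If the share lying outside the bed differs between MF and unifocal patients, the comparison that objective 4 asks for is distorted as well. The protocol also aims to produce recommendations for managing MF disease, so a reader would take objective 4 as evidence on whether conservation is safe.

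The definition speaks of one tumor bed. It does not say how to treat a patient with several excised foci, which is the population of interest.

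**Working it through.** **Text check.** For a patient treated by BCS, each possible first relapse is placed in the written categories:

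- in the tumor bed: local;
- in the ipsilateral axillary, supraclavicular or internal mammary nodes: regional;
- distant: distant metastasis;
- in the same breast but outside the bed: no category.

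Nothing in the Group B Methods or the SAP fills the last line. After mastectomy the whole field counts, so the omission concerns BCS patients only. Overall survival does not depend on these definitions.

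**Is there a figure to reproduce?** No. Neither document gives a number of patients, an event count, a recurrence rate, a target effect or a power. What follows is illustration, and every input is my assumption.

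**Rate after BCS.** Let s be the share of in-breast relapses outside the bed.

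Reported rate = true rate × (1 − s).

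With a true rate of 5%: s = 10% gives 5% × 0.9 = 4.5%; s = 40% gives 5% × 0.6 = 3.0%.

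**MF versus unifocal after BCS.** Let H be the true in-breast hazard ratio, and sM and sU the out-of-bed shares in MF and unifocal patients. For rare events,

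observed ratio = H × (1 − sM) / (1 − sU).

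The same expression holds for a ratio of relapse proportions. With H = 2.0 and sU = 20%:

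- sM = 10%: 2.0 × 0.9 / 0.8 = 2.25 (exaggerated)
- sM = 20%: 2.0 × 0.8 / 0.8 = 2.00 (unchanged)
- sM = 40%: 2.0 × 0.6 / 0.8 = 1.50
- sM = 60%: 2.0 × 0.4 / 0.8 = 1.00 (effect gone)

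With H = 1.5 and sU = 20%, sM = 40% gives 1.5 × 0.6 / 0.8 = 1.125, and sM = 60% gives 1.5 × 0.4 / 0.8 = 0.75, which is below 1.

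Over sU = 10-30% and sM = 10-60%, a true 2.0 appears as anything from 2.0 × 0.4 / 0.9 = 0.89 to 2.0 × 0.9 / 0.7 = 2.57. A true 1.5 appears as 0.67 to 1.93. With a whole-breast event, the ratio is H in every case.

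**Equal shares still lose events.** Take H = 2.0, 20% of patients MF, two-sided 0.05 (the SAP gives 0.05 but no sidedness) and 80% power. Schoenfeld's formula gives (1.96 + 0.84)² / (0.2 × 0.8 × (ln 2)²), which is 103 events rounded up. Losing 10% of them leaves 93 events and 76% power. Losing 50% leaves 52 events and 51% power.

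**The case against.** **The wording may be shorthand.** The sentence sets the tumor bed against the mastectomy field and may simply mean the operated area. Investigators may have counted every in-breast relapse. This stands as a limit: the documents do not show how such relapses were coded, or whether any occurred. A reader might infer that events were in fact omitted, and the text does not support that. It remains a written rule that a literal coder would follow.

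**The Introduction is not an end point.** The in-breast worry is reported there as a perceived risk behind a traditional view, for MF and MC disease together. The objectives concern MF disease, which the same section describes as typically "two or more synchronous areas of disease confined within the same quadrant". Some relapses in MF patients would therefore lie in or near the bed and be counted. Both points are fair. They reduce the likely loss without removing the gap.

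**A hidden MF excess.** A reader might infer that the definition conceals a higher relapse risk in MF patients. That needs a larger out-of-bed share in MF than in unifocal patients, which no passage gives. The ratio can equally be unchanged or exaggerated.

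**Unequal capture after the two operations.** A reader might also infer that counting the whole field after mastectomy but only the bed after BCS biases any comparison that combines operations. That would need MF and unifocal patients to differ in mastectomy use and the analysis to ignore operation. The documents give no such figures. They record surgery as a variable and do not list the Cox covariates. I place no weight on this argument.

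**The analysis for objective 4 is not specified.** No passage describes an MF versus unifocal model restricted to BCS, and the SAP does not mention the Kaplan-Meier or Cox methods. The hazard ratios above therefore illustrate the question asked and do not describe a planned result.

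**Conclusion.** The point holds as a statement about the end point. As written, a relapse in the conserved breast outside the tumor bed is not an event. Objective 4 is affected directly, and the loco-regional part of objective 5 is affected for BCS patients only.

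The size and direction of any bias cannot be derived from the documents. The in-breast relapse rate after BCS is understated if any out-of-bed relapse occurred and the rule was followed. The MF versus unifocal comparison can move either way, including below 1, or not at all.

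A reader might infer that the primary objective is compromised too. That follows only if the Group A definition carries over to Group B. This is the natural reading, but the protocol does not state it.

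Confidence is high for the gap in the wording and low for its consequence. It should be fixed because it concerns the event on which objective 4 rests.

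**What to change.** Define local recurrence after BCS as any recurrence in the ipsilateral breast. Leave the mastectomy wording as it is, and state that the definition applies to Groups A and B.

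For each in-breast event after BCS, record two items:

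- site: tumor bed (any of the beds when several foci were excised), elsewhere in the breast, or not recorded;
- whether the event was labelled a new primary.

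Group A is a chart series ("their data are retrospectively reviewed and analyzed") and the SAP describes the data as already collected. The report should therefore label this as a change of definition made after data collection. Two further sets of results belong beside the main one: events under the tumor-bed definition as now written, and in-breast events excluding flagged new primaries. The first preserves the written rule if it was intended. The second shows how far new primaries drive the result. If the investigators already counted every in-breast relapse, they should say so, and the change is then mainly to the text.

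The cost is about two sentences in the Methods, two abstracted fields and a re-check of some 2010-2015 charts. Site will be missing in some of them, and the reported local recurrence rate may rise.

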Furthermore, Multifocal/MC disease has also been implicated as a prognostic factor. Studies have demonstrated that MF/MC cancers may have an increased susceptibility to axillary lymph node (LN) involvement. It is unclear whether this is due to inaccurate staging by using the largest tumor dimension or if these malignancies have an inherent biologic capacity to spread.

In addition, MF/MC disease has been found to correlate with known risk factors suggesting an aggressive biology such as young age, higher grade, negative hormone receptor status, negative HER-2 status, and lymphovascular invasion. Yet the impact on outcomes is unclear with studies demonstrating mixed results.

Unfortunately, due to the relatively heterogeneous cohort of patients with MF/MC breast cancer, standardized guidelines are not well established.

Therefore, it remains unclear whether MF/MC breast cancers should be considered a separate category with a potentially unfavourable impact on prognosis and whether these lesions require specific treatment with more extensive surgery or committed adjuvant therapies.

[name]

[figure not shown]
✓

✓

✓

The present study is directed to analyze, in a large retrospective series of breast cancer patients treated at a single institution, the impact of (MF) breast cancers on the long-term survival in relation to other known pathological and clinical factors and to the type of treatment received. Furthermore, the prospective limb of this study is directed to evaluate the outcomes of oncoplastic techniques as a surgical management for multifocal breast cancer.

[name]

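### Group A's Cox model names local recurrence while the log-rank analysis it follows, and secondary objective 5, use loco-regional recurrence, so objective 5 has no adjusted analysis as written

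*Protocol*

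**What the plan says.** All of the recurrence analyses are in the protocol, METHODS, Group (A).

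- **Definitions.** Local and regional recurrence are defined separately: "Local recurrence is defined as recurrence in the original tumor bed (for BCS) or field of mastectomy". Relapse in the axillary, supraclavicular or internal mammary nodes on the same side is classed as regional.
- **Unadjusted step.** "Loco-regional recurrence-free survival of patients who are pathologically multi-focal and uni-focal will be estimated using the Kaplan-Meier method", with log-rank comparisons. The text calls this the univariable analysis "of risk factors for loco-regional recurrence among multi-focal and uni-focal breast cancer patients".
- **Adjusted step.** "Associations with local recurrence in uni-focal and multi-focal breast cancer patients are further evaluated using multivariable Cox proportional hazards regression model".
- **Distal recurrence.** In the unadjusted step, "Distal recurrence-free survival for both groups will be analyzed using the same test". In the adjusted step, "Associations with distal recurrence uni-focal and multi-focal breast cancer patients will be further evaluated using multivariable Cox regression model".

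Under Secondary objectives, item 5 reads "Exploring the association between multifocality and overall survival and loco-regional relapse". Item 4 asks about local relapse, but only in patients treated with BCT.

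The SAP (Data Management and Analysis) lists frequencies and percentages, then chi-square, Fisher's exact and Monte Carlo tests. It names no Kaplan-Meier, log-rank or Cox analysis.

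**The concern.** A Cox model that further evaluates a univariable result should carry the same endpoint, so that a change between the two estimates can be put down to adjustment. Here the endpoint changes along with the adjustment. If a loco-regional difference on the log-rank test shrank in the Cox model, a reader could not tell whether covariates explained it or nodal relapses had dropped out of the event count.

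The second consequence concerns objective 5. Group A is a retrospective cohort in which treatment and focality were not assigned. The Introduction reports that multifocal and multicentric disease correlates with younger age, higher grade, receptor and HER-2 status, and lymphovascular invasion. On the protocol's own account, then, an unadjusted multifocal versus unifocal comparison is open to confounding, and that is the only analysis planned for loco-regional relapse.

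**Working it through.** The documents give no figure to reproduce: no Group A sample size, event count, recurrence rate or hazard ratio. The check is a cross-tabulation of endpoints against objectives and analyses, all taken from the protocol (Secondary objectives; METHODS, Group (A)).

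| Endpoint | Secondary objective naming it | Unadjusted analysis | Cox model |
|---|---|---|---|
| Loco-regional | 5 | Kaplan-Meier and log-rank | none |
| Local | 4, BCT patients only | none of its own | yes, not limited to BCT |
| Regional | none on its own | only inside loco-regional | none |
| Distal | none | yes | yes |

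1. Distal recurrence has the same endpoint in both steps. This shows the intended pattern: a univariable analysis, then a Cox model for the same outcome.
2. The other pair breaks the pattern. Loco-regional recurrence has only the unadjusted step, and local recurrence has only the adjusted one.
3. Under the protocol's definitions, a patient whose first relapse is in the axilla is an event in the loco-regional Kaplan-Meier curve but not in the local-recurrence Cox model. The protocol also treats loco-regional recurrence or distant metastasis as an end point for follow-up. Such a patient would therefore leave the local model without an event, and no censoring or competing-risk rule is given.
4. The distal Cox model does not obviously fill the gap. Distal recurrence is not defined, but the separate regional definition and the mention of distant metastases make it unlikely to include regional nodes.
5. The SAP adds no survival model, so it does not fill the gap either.

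The size of the discrepancy can be put only in symbols. With constant hazards, let p be the local share of the loco-regional hazard in the unifocal group. Then

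HR(loco-regional) = p × HR(local) + (1 − p) × HR(regional).

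If the two component hazard ratios are equal, the loco-regional and local hazard ratios agree and the local model loses only precision, because it has fewer events. If they differ, the two hazard ratios differ, in either direction. The documents give none of p, HR(local) or HR(regional), so no number can be attached.

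**The case against.** The strongest reply is that *local* is a loose word for *loco-regional*. The Cox sentence says the associations are evaluated further, and the only non-distal analysis it can follow is the loco-regional one; the distal sentences run in parallel. That reading is credible. It does not remove the point, because an analyst who applies the protocol's definitions would leave nodal relapse out.

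A local-recurrence model also has a purpose of its own. The Introduction gives a perceived higher risk of recurrence in the breast as the first reason for avoiding conservation, and objective 4 asks about local relapse. This stands, and the fix keeps such a model. But objective 4 is limited to BCT patients, the Cox sentence is not, and neither serves objective 5.

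Objective 5 is secondary and exploratory, and it promises no adjusted estimate. This also stands, and it limits how serious the point is.

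Two stronger readings are tempting. A reader might infer that nodal relapse is where an effect of multifocality is most likely, since the Introduction says "MF/MC cancers may have an increased susceptibility to axillary lymph node (LN) involvement". That sentence is about nodal involvement, not relapse after treatment. The text that follows allows that inaccurate staging may explain it, and calls the effect on outcomes unclear. A reader might also infer that the Cox hazard ratio will be too low, or that a significant log-rank result will vanish. The documents give no event split or component hazard ratios, so they support neither.

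**Conclusion.** The concern holds as an endpoint mismatch between the unadjusted and adjusted Group A analyses. Taken as written, objective 5's loco-regional endpoint has no adjusted analysis, and the log-rank and Cox results are not comparable. This rests on reading *local* as the protocol defines it. If it is a slip, the analysis intended is sound and only the text is wrong, but it must still be corrected.

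Its size is unknown, because the event counts needed are not in the documents. A reader should not take the mismatch as evidence of a deliberate choice to exclude nodal relapse, nor of bias in a known direction.

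The mismatch lies within the protocol. Under the SAP taken alone, no endpoint has a survival model at all, so rewording the protocol would not be enough. The correction should be made, in proportion to a secondary, exploratory objective.

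**What to change.** 1. In the protocol, METHODS, Group (A), name loco-regional recurrence (local or regional, as defined there) as the endpoint of the multivariable Cox model for objective 5, matching the Kaplan-Meier and log-rank endpoint. Report the unadjusted and adjusted results for it side by side.
2. Keep a separate Cox model for local recurrence, restricted to BCT patients, for objective 4. State how a first relapse at another site is handled in it.
3. List the Kaplan-Meier, log-rank and Cox analyses in the SAP, each with its endpoint and population.

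The cost is one extra model run and a short text change in each document. No new data are needed: the protocol already records loco-regional recurrence and separates local from regional sites. The SAP is dated December 2, 2019 and is written in the past tense. If the analysis had already been run, the added model should be reported as added afterwards.
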